12. STUDY OVERSIGHT AND DATA REPORTING / REGULATORY REQUIREMENTS

Adverse event lists, guidelines, and instructions for AE reporting can be found in Section 7.0 (Adverse Events: List and Reporting Requirements).

12.1 Study Oversight

This protocol is monitored at several levels, as described in this section. The Protocol Principal Investigator is responsible for monitoring the conduct and progress of the clinical trial, including the ongoing review of accrual, patient-specific clinical and laboratory data, and routine and serious adverse events; reporting of expedited adverse events; and accumulation of reported adverse events from other trials testing the same drug(s). The Protocol Principal Investigator and statistician have access to the data at all times through the CTMS web-based reporting portal.

During the initial phase of the study (before the interim futility analysis), the Protocol Principal Investigator will have, at a minimum, quarterly conference calls with the Study Investigators to review accrual, progress, and pharmacovigilance. Decisions to proceed with the study beyond the interim analysis will require sign-off by the Protocol Principal Investigator and the Protocol Statistician.

All Study Investigators at participating sites who register/enroll patients on a given protocol are responsible for timely submission of data via Medidata Rave and timely reporting of adverse events for that particular study. This includes timely review of data collected on the electronic CRFs submitted via Medidata Rave.

All studies are also reviewed in accordance with the enrolling institution's data safety monitoring plan.

12.2 Data Reporting

Data collection for this study will be done exclusively through Medidata Rave. Access to the trial in Rave is granted through the iMedidata application to all persons with the appropriate roles assigned in the Regulatory Support System (RSS). To access Rave via iMedidata, the site user must have an active CTEP IAM account (check at https://ctepcore.nci.nih.gov/iam) and the appropriate Rave role (Rave CRA, Rave Read-Only, Rave CRA (Lab Admin), Rave SLA, or Rave Investigator) on either the LPO or participating organization roster at the enrolling site. To the hold Rave CRA role or Rave CRA (Lab Admin) role, the user must hold a minimum of an AP registration type. To hold the Rave Investigator role, the individual must be registered as an NPIVR or IVR. Associates can hold read-only roles in Rave.

Upon initial site registration approval for the study in RSS, all persons with Rave roles assigned on the appropriate roster will be sent a study invitation e-mail from iMedidata. To accept the invitation, site users must log into the Select Login (https://login.imedidata.com/selectlogin) using their CTEP-IAM user name and password, and click on the "accept" link in the upper right-corner of the iMedidata page. Please note, site users will not be able to access the study in Rave until all required Medidata and study specific trainings are completed. Trainings will be in the form of electronic learnings (eLearnings), and can be accessed by clicking on the link in the upper right pane of the iMedidata screen.

Users that have not previously activated their iMedidata/Rave account at the time of initial site registration approval for the study in RSS will also receive a separate invitation from iMedidata to activate their account. Account activation instructions are located on the CTSU website, Rave tab under the Rave resource materials (Medidata Account Activation and Study Invitation Acceptance). Additional information on iMedidata/Rave is available on the CTSU members' website under the Rave tab or by contacting the CTSU Help Desk at [name] or by e-mail at [contact].

12.2.1 Method

This study will be monitored by the Clinical Trials Monitoring Service (CTMS). Data will be submitted to CTMS at least once every two weeks via Medidata Rave (or other modality if approved by CTEP). Information on CTMS reporting is available at: http://www.theradex.com/clinicalTechnologies/?National-Cancer-Institute-NCI-11. On-site audits will be conducted on an 18-36 month basis as part of routine cancer center site visits. More frequent audits may be conducted if warranted by accrual or due to concerns regarding data quality or timely submission. For CTMS monitored studies, after users have activated their accounts, please contact the Theradex Help Desk at [contact] or by email at [contact] for additional support with Rave and completion of CRFs.

12.2.2 Responsibility for Data Submission

For ETCTN trials, it is the responsibility of the PI(s) at the site to ensure that all investigators at the ETCTN Sites understand the procedures for data submission for each ETCTN protocol and that protocol specified data are submitted accurately and in a timely manner to the CTMS via the electronic data capture system, Medidata Rave.

Data are to be submitted via Medidata Rave to CTMS on a real-time basis, but no less than once every 2 weeks. The timeliness of data submissions and timeliness in resolving data queries will be tracked by CTMS. Metrics for timeliness will be followed and assessed on a quarterly basis. For the purpose of Institutional Performance Monitoring, data will be considered delinquent if it is greater than 4 weeks past due.

Data from Medidata Rave and CTEP-AERS is reviewed by the CTMS on an ongoing basis as data is received. Queries will be issued by CTMS directly within Rave. The queries will appear on the Task Summary Tab within Rave for the CRA at the ETCTN to resolve. Monthly web-based reports are posted for review by the Drug Monitors in the IDB, CTEP. Onsite audits will be conducted by the CTMS to ensure compliance with regulatory requirements, GCP, and NCI policies and procedures with the overarching goal of ensuring the integrity of data generated from NCI-sponsored clinical trials, as described in the ETCTN Program Guidelines, which may be found on the CTEP (http://ctep.cancer.gov/protocolDevelopment/electronic_applications/adverse_events.htm) and CTSU websites.

An End of Study CRF is to be completed by the PI, and is to include a summary of study endpoints not otherwise captured in the database, such as (for phase 1 trials) the recommended phase 2 dose (RP2D), and a description of any dose-limiting toxicities (DLTs). CTMS will utilize a core set of eCRFs that are Cancer Data Standards Registry and Repository (caDSR) compliant (http://cbiit.nci.nih.gov/ncip/biomedical-informaticsresources/interoperability-and-semantics/metadata-and-models). Customized eCRFs will be included when appropriate to meet unique study requirements. The PI is encouraged to review the eCRFs, working closely with CTMS to ensure prospectively that all required items are appropriately captured in the eCRFs prior to study activation. CTMS will prepare the eCRFs with built-in edit checks to the extent possible to promote data integrity.

CDUS data submissions for ETCTN trials activated after March 1, 2014, will be carried out by the CTMS contractor, Theradex. CDUS submissions are performed by Theradex on a monthly basis. The trial's lead institution is responsible for timely submission to CTMS via Rave, as above.

Further information on data submission procedures can be found in the ETCTN Program Guidelines

(http://ctep.cancer.gov/protocolDevelopment/electronic_applications/adverse_events.htm).

12.3 CTEP Multicenter Guidelines Not Applicable.

12.4 Collaborative Agreements Language

The agent(s) supplied by CTEP, DCTD, NCI used in this protocol is/are provided to the NCI under a Collaborative Agreement (CRADA, CTA, CSA) between the Pharmaceutical Company(ies) (hereinafter referred to as "Collaborator(s)") and the NCI Division of Cancer Treatment and Diagnosis. Therefore, the following obligations/guidelines, in addition to the provisions in the "Intellectual Property Option to Collaborator"

(http://ctep.cancer.gov/industryCollaborations2/intellectual_property.htm) contained within the terms of award, apply to the use of the Agent(s) in this study:

- Agent(s) may not be used for any purpose outside the scope of this protocol, nor can Agent(s) be transferred or licensed to any party not participating in the clinical study. Collaborator(s) data for Agent(s) are confidential and proprietary to Collaborator(s) and shall be maintained as such by the investigators. The protocol documents for studies utilizing Agents contain confidential information and should not be shared or distributed without the permission of the NCI. If a copy of this protocol is requested by a patient or patient's family member participating on the study, the individual should sign a confidentiality agreement. A suitable model agreement can be downloaded from: http://ctep.cancer.gov.
- 2. For a clinical protocol where there is an investigational Agent used in combination with (an)other Agent(s), each the subject of different Collaborative Agreements, the access to and use of data by each Collaborator shall be as follows (data pertaining to such combination use shall hereinafter be referred to as "Multi-Party Data"):
 - a. NCI will provide all Collaborators with prior written notice regarding the existence and nature of any agreements governing their collaboration with NCI, the design of the proposed combination protocol, and the existence of any obligations that would tend to restrict NCI's participation in the proposed combination protocol.
 - b. Each Collaborator shall agree to permit use of the Multi-Party Data from the clinical trial by any other Collaborator solely to the extent necessary to allow said other Collaborator to develop, obtain regulatory approval or commercialize its own Agent.
 - c. Any Collaborator having the right to use the Multi-Party Data from these

trials must agree in writing prior to the commencement of the trials that it will use the Multi-Party Data solely for development, regulatory approval, and commercialization of its own Agent.

- 3. Clinical Trial Data and Results and Raw Data developed under a Collaborative Agreement will be made available to Collaborator(s), the NCI, and the FDA, as appropriate and unless additional disclosure is required by law or court order as described in the IP Option to Collaborator (http://ctep.cancer.gov/industryCollaborations2/intellectual_property.htm). Additionally, all Clinical Data and Results and Raw Data will be collected, used and disclosed consistent with all applicable federal statutes and regulations for the protection of human subjects, including, if applicable, the *Standards for Privacy of Individually Identifiable Health Information* set forth in 45 C.F.R. Part 164.
- 4. When a Collaborator wishes to initiate a data request, the request should first be sent to the NCI, who will then notify the appropriate investigators (Group Chair for Cooperative Group studies, or PI for other studies) of Collaborator's wish to contact them.
- 5. Any data provided to Collaborator(s) for Phase 3 studies must be in accordance with the guidelines and policies of the responsible Data Monitoring Committee (DMC), if there is a DMC for this clinical trial.
- 6. Any manuscripts reporting the results of this clinical trial must be provided to CTEP by the Group office for Cooperative Group studies or by the principal investigator for non-Cooperative Group studies for immediate delivery to Collaborator(s) for advisory review and comment prior to submission for publication. Collaborator(s) will have 30 days from the date of receipt for review. Collaborator shall have the right to request that publication be delayed for up to an additional 30 days in order to ensure that Collaborator's confidential and proprietary data, in addition to Collaborator(s)'s intellectual property rights, are protected. Copies of abstracts must be provided to CTEP for forwarding to Collaborator(s) for courtesy review as soon as possible and preferably at least three (3) days prior to submission, but in any case, prior to presentation at the meeting or publication in the proceedings. Press releases and other media presentations must also be forwarded to CTEP prior to release. Copies of any manuscript, abstract and/or press release/ media presentation should be sent to:

Email: [contact]

The Regulatory Affairs Branch will then distribute them to Collaborator(s). No publication, manuscript or other form of public disclosure shall contain any of Collaborator's confidential/ proprietary information.

13. STATISTICAL CONSIDERATIONS

13.1 Study Design/Endpoints

13.1.1 Overview

This is a phase 2 study designed to evaluate the safety and efficacy of the addition of nivolumab to CDX-1127 (varilumab) for patients with advanced high-grade B-cell NHL. The study will utilize a randomized phase 2 study design to determine the antitumor activity of combination therapy with CDX-1127 (varilumab) and nivolumab (Group 2; experimental group) as compared to nivolumab alone (Group 1; control group), where response will be evaluated based on the LYRIC response criteria.

13.1.2 Primary Endpoint

The primary endpoint of this trial is the overall response rate, which will be compared between the two groups. A response will be defined as an objective status of PR or CR for patients evaluated by CT-based criteria and CMR or PMR for patients evaluated by PET-CT based criteria. All patients meeting the eligibility criteria who have signed a consent form and have begun treatment will be evaluable for overall response.

13.1.3 Statistical Design

Decision Rule: A randomized trial comparing combination therapy with CDX-1127 (varlilumab) and nivolumab as compared to nivolumab alone will be conducted as described by Rubinstein. We will enter 48 evaluable patients on each group of the study using a 1:1 randomization scheme where patients are stratified based on age (< 65 vs. \geq 65 years), previous autologous stem cell transplant (yes vs. no), and diagnosis category per Section 3.1.1 (A vs. B). Randomization will be done using a (stratified) permuted block design with randomly varying block sizes. A sample size of 48 patients per group provides 80% power to detect an improvement in response rate from 25% to 45%, using a one-sided test at a significance level of 0.15 (nQuery 7.0).

This estimated response rate is based on the clinical efficacy demonstrated by Nivolumab in the phase II trial (Lesokhin et al, JCO 2016). In that study 11 patients with DLBCL were treated with Nivolumab, of which 4 (36%) achieved an objective response. Nonetheless, at the time of publication only 1 of those maintained a response while 2 were still being followed (3 of 11 or 27%). Unpublished data from a larger phase 2 trial appears to have a low response rate for nivolumab alone with an overall response rate that appears to be < 20%. We therefore selected 25% as our best estimate of response for nivolumab alone.

Interim Analysis Decision Rule: An interim analysis with a futility rule will be performed after half of the patients (24 patients in each group) have completed their first radiologic scan after 3 cycles (12 weeks of treatment or up to 20 weeks if treatment delays occurred). At the time of the interim analysis, we will compare the response rate of Group 2 the experimental group to Group 1 the control group. If the response rate in Group 2 the experimental group is less than the response rate in Group 1 the control group, we will consider this early evidence that the Group 2 the experimental group does not have a higher overall response rate and accrual will be terminated. Otherwise, we will continue accrual (Wieand *et al.*, 1994)

Final Decision Rule: The final analysis will take place after all 48 evaluable patients in each group have been followed for at least 6 months. The response rates will be compared between the two groups using Fisher's exact test. If the response rate is higher in Group 2 the experimental group, where the p-value < 0.15, this will be considered sufficient evidence that Group 2 the experimental group may be recommended for further testing in subsequent studies. Otherwise, we will conclude that there is not statistical evidence of superiority of the experimental regimen.

Over Accrual: If more than the target number of patients are accrued, the additional patients will not be used to evaluate the stopping rule or used in any decision making process however, they will be included in final point estimates and confidence intervals.

NOTE: The trial will not be halted while the first 24 patients in each group are evaluated for the interim analysis. However, if the accrual is especially rapid, we may temporarily suspend accrual to prevent missing important acute toxicity patterns.

Other Considerations: Toxicity, quality/duration of response, and patterns of treatment failure observed in this study, as well as scientific discoveries or changes in standard care will be taken into account in any decision to terminate the study.

13.1.4 Analysis Plan

The analysis for this trial will commence at planned time points and at the time the patients have become evaluable for the primary endpoint. Such a decision will be made by the Statistician and Study Chair, in accord with ETCTN Standard Operating Procedures, availability of data for secondary endpoints (eg, laboratory correlates), and the level of data maturity. It is anticipated that the earliest date in which the results will be made available via manuscript, abstract, or presentation format is when the last patient has been followed for at least 6 months.

13.1.5 Primary Endpoint

Definition: The primary endpoint of this trial is the overall response rate, which will be compared between the two arms. A response will be defined as an objective status of PR or CR for patients evaluated by CT-based criteria and CMR or PMR for patients evaluated by PET-CT based criteria. All patients meeting the eligibility criteria who have signed a consent form and have begun treatment will be evaluable for overall response.

Estimation: The proportion of successes will be estimated in each arm by the number of successes divided by the total number of evaluable patients. Exact binomial ninety-five percent confidence intervals for the true success proportion will be calculated in

each arm. Comparison of overall response rates between the two treatment groups will be performed using a one-sided Fisher's exact test at significance level 0.15.

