13.3 Stratification Factors

- 13.3.1 Age group: < 65 years or ≥ 65 years
- 13.3.2 Previous autologous stem cell transplant: yes vs. no
- 13.3.3 Diagnosis category (per section 3.1.1): Category A vs. Category B

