13.4.2 Survival Time

Survival time is defined as the time from randomization to death due to any cause. The distribution of survival time will be estimated using the method of Kaplan-Meier. The comparison of overall survival between two treatment arms will be based on the log-rank test.

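### Fisher's exact test spends only about 0.10 of the planned one-sided 0.15; Boschloo's exact test would add about 3 points of power with the same patients

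*Combined protocol and SAP*

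**What the plan says.** The primary comparison is set in two places. The final decision rule in section 13.1.3 says "The response rates will be compared between the two groups using Fisher's exact test" and recommends the combination for further testing if its response rate is higher and p < 0.15. Section 13.1.5 adds the sidedness: "Comparison of overall response rates between the two treatment groups will be performed using a one-sided Fisher's exact test at significance level 0.15".

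The sample size statement in section 13.1.3 reads "A sample size of 48 patients per group provides 80% power to detect an improvement in response rate from 25% to 45" per cent, one-sided at 0.15. The 25% control rate was chosen between two pieces of evidence in the same section: a small published DLBCL cohort of 11 patients, "of which 4 (36%) achieved an objective response", and unpublished data with "an overall response rate that appears to be < 20" per cent. A futility look at 24 per arm stops accrual if the experimental response rate is below the control rate.

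Patients are allocated "using a 1:1 randomization scheme where patients are stratified based on age", prior transplant and diagnosis category. Section 13.3 lists the same factors, for example "Previous autologous stem cell transplant: yes vs. no". The analysis sections do not mention them again. For survival, section 13.4.2 says "The comparison of overall survival between two treatment arms will be based on the log-rank test", and section 13.4.3 treats progression-free survival the same way.

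The plan does not give the actual error rate of Fisher's test at this sample size and does not consider an unconditional exact test.

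**The concern.** The design accepts a one-sided error rate of 0.15, which is permissive, to keep a screening trial small. Fisher's test conditions on the total number of responders. Its p-value therefore moves in coarse steps, and the realised error rate falls short of the nominal level. The trial agrees to a 15% false-positive risk but does not get all the power that this risk could buy.

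The decision can turn on a single responder. Under section 13.1.3, a result that misses p < 0.15 leads to the conclusion that there is no statistical evidence of superiority. An exact test that uses more of the 0.15 lowers that bar by one patient in most realistic outcomes.

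A smaller, separate gap is that randomisation is stratified by three factors and no analysis reflects this.

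**Working it through.** **Inputs** (section 13.1.3 unless noted): 48 evaluable patients per arm, 1:1; control 25%, experimental 45%; one-sided 0.15; Fisher's test with p < 0.15 (also section 13.1.5); futility look at 24 per arm, stopping if experimental responders are fewer than control responders.

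**Method.** Let C and E be the responders in the control and experimental arms, independent Binomial(48, p). The one-sided Fisher p-value is P(X ≥ E), with X hypergeometric: 48 drawn from 96, of which C + E are responders. The rejection probability is the sum, over all 49 × 49 outcomes, of Bin(C; 48, p_C) × Bin(E; 48, p_E) × 1{reject}. Size sets p_C = p_E; power sets 25% and 45%.

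**Step 1: the plan's own figure.** Fisher at p < 0.15 gives power 0.8094, so the stated 80% is reproduced. The continuity-corrected normal formula gives 49 per arm, which also agrees. The uncorrected formula gives 40.

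**Step 2: Fisher's actual size.** It is 0.096 at a common rate of 20%, 0.100 at 25%, 0.110 at 30%, and 0.115 at its maximum (near 35% or 65%). The unused share is (0.15 − 0.100)/0.15 = 33% at the planning rate and (0.15 − 0.115)/0.15 = 23% in the worst case.

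**Step 3: Boschloo's test.** It uses the Fisher p-value as the test statistic. It rejects below the largest cut-off whose size, maximised over all common response rates, is at most 0.15. Here that means rejecting when Fisher's p ≤ 0.1932.

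**Step 4: the look.** Outcomes with E < C at 24 per arm are removed, and the remainder is combined with the second 24 per arm.

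| 48 per arm | Fisher | Boschloo | Difference |
|---|---|---|---|
| Power, 25% vs 45%, no look | 0.8094 | 0.8376 | +2.8 points |
| Power, 25% vs 45%, with look | 0.7983 | 0.8241 | +2.6 points |
| Power, 20% vs 40%, with look | 0.8160 | 0.8554 | +3.9 points |
| Power, 36% vs 56%, with look | 0.7426 | 0.7915 | +4.9 points |
| Size at 25%, no look | 0.100 | 0.143 | |
| Size at 25%, with look | 0.097 | 0.137 | |
| Maximum size, no look | 0.115 | 0.147 | |
| Maximum size, with look | 0.111 | 0.140 | |

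The 20% and 36% rows use the other control rates that section 13.1.3 mentions and keep the 20-point improvement.

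**Step 5: in patients.** With 17/48 versus 12/48 responders, Fisher's p is 0.187 (fails) and Boschloo's is 0.142 (passes); Fisher needs 18/48. For 4 to 21 control responders, the bar drops by one patient except at 6, 14, 15 and 16, where it does not move. To match Boschloo's power at 48 per arm, Fisher needs 57 per arm (56 gives 0.8359; 57 gives 0.8424), or 2 × (57 − 48) = 18 more patients.

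**Step 6: a plain z-test is not a substitute.** The uncorrected pooled z-test has a maximum size of 0.164, above 0.15.

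**Step 7: stratification.** The documents give no stratum data, so this step rests on assumptions: 50% aged 65 or over, 30% with prior transplant, 20% in Category A; log-odds effects of 0, −0.5 to −0.7, or −0.8 to −1.0; permuted blocks of 2 or 4; 12,000 simulated trials per scenario. The uncorrected Cochran-Mantel-Haenszel (CMH) test minus the unstratified z-test gives −0.4, +0.2 and +1.0 points of power without the look, and −0.3, +0.1 and +0.9 with it. The CMH test's size ran from 0.146 to 0.155 across simulations without the look.

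**The case against.** The strongest reply is that nothing is broken. Fisher's test is named, one-sided and valid, and 48 per arm delivers the stated power. That stands, and it is why this is an optional improvement.

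Second, the gain comes from spending more of the error rate. At the planning point, false-positive risk rises by 4.3 points (0.100 to 0.143) for 2.8 points of power. A sponsor may prefer the lower realised risk when the nominal 0.15 is already generous. This is a fair preference, but the plan does not state it. The design set 0.15 as its tolerance, and Boschloo's test stays within it.

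Third, the 18-patient comparison matches power at the same nominal level but not at the same realised size: Fisher at 57 per arm has size 0.111 at 25%, against 0.143 for Boschloo at 48. It also turns on 0.2 points, since Fisher at 56 per arm gives 83.6%. It should be read with both qualifications.

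Fourth, section 12.1 gives the Protocol Principal Investigator and the statistician access to the data at all times, and the interim look compares response by arm. A move to a more liberal primary test after such access would cost credibility. The documents do not show how far the trial has progressed. This makes the timing condition essential.

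Fifth, the stratification gap has almost no measurable effect on power and rests on assumed strata. That is correct, so it supports secondary analyses only.

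**Conclusion.** The point holds as an efficiency improvement; it is not an error in the plan. At the design's own assumptions, Fisher's test uses about 0.10 of the 0.15, and Boschloo's test adds 2.8 points of power (2.6 with the futility look). The gain is larger at the other control rates the plan cites, and it reaches about 5 points if the arms end at sizes such as 47 and 49. With the look included, Fisher's power is 79.8%, marginally under the stated 80%; Boschloo's is 82.4%. Boschloo's test rejects whenever Fisher's does.

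The Fisher and Boschloo figures are exact and depend only on the arm sizes, response rates and futility rule in section 13.1.3. The stratification figures depend on assumed prevalences and effects.

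**What to change.** Before any outcome data by arm are seen, amend the final decision rule in section 13.1.3 and the estimation paragraph in section 13.1.5:

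- **Primary test:** Boschloo's exact unconditional test, one-sided at 0.15, computed at the actual arm sizes. State the realised size and power, including the futility look.
- **Sensitivity analysis:** the one-sided Fisher's exact test as now written.
- **Supporting analyses by the three factors in section 13.3:** for response, a CMH test without continuity correction and a stratified risk difference with its confidence interval; for progression-free and overall survival, stratified log-rank tests. No power gain is claimed for the stratified log-rank tests.

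If outcome data by arm have already been seen, the timing condition is not met and Fisher's test should remain primary.

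The cost is SAP wording and a few lines of code, with no extra patients or data. The downsides to record are:

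- The actual false-positive risk at 25% rises from 0.100 to 0.143.
- The uncorrected CMH test is asymptotic and can slightly exceed 0.15, so it must stay supporting.
- Three binary factors make 2 × 2 × 2 = 8 strata, and some cells will be sparse.
- A continuity-corrected CMH test would give only −0.5 to +1.1 points against Fisher's test, so the correction must be explicitly excluded.
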